[figure not shown]
¹ The bloc 1 will not be included in the final statistical analysis because is considered as a training bloc. This choice in accordance to the potential biases related to the increase of the sympathetic activity at the beginning of the task caused by a simple moving to action following the resting period.

second session, a short training session of the biofeedback [BFB] technique will be done and the software using for the biofeedback training will be supplied to each participant included in the experimental group to allowed to us to practice BFB by their self at home. The installation of the program and the explanations needed for using it, will be done during the second session (T2). The BFB software (Emwave Pro®) includes a photoplethysmography sensor that can be positioned on the earlobe. The participants will have to practice the biofeedback technique the next 24 days (3X5 min/day).

The period (24 days) between the second session and the third session (T2-T3) will be considered as the intervention period. At the end of the second session (T2), the participants will be separated into two inter-subject groups: an experimental group performing BFB technique (3X5 min per day) in the intervention period (T2-T3) and a control group not performing a specific exercise in the intervention period (T2-T3). The first 40 participants (20 IBS / 20 PNES) will be included into the experimental group (BFB training) whereas the last 10 participants (5 IBS / 5 PNES) will be included into the control group (no training). The participants won't be informed of the condition to which they belong. We will measure the parameters of interest before (T2) and at the end of the intervention period (T3). During the intervention period, all the participants will have to answer to online questionnaires (BVAQ-B, LES, DHS) aiming to examine the psychological profile (alexithymia, traumatic events).

The third session (T3), T2 + 24 days, will be similar of the two previous sessions. We will use the same questionnaires and will record the same electrophysiological parameters. Finally, a debriefing will be done at the end of the session for each participant. The session will be considered as the end of the study visit.

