- SDNN (standard deviation of all NN intervals) temporal-domain parameter
- EDR (ECG-derived-respiration)

GSR (tonic GSR / phasic GSR):

- SCR frequency: number of the spontaneous galvanic skin responses by periods
- SCR amplitude: amplitude of the spontaneous galvanic skin responses by periods
- Integrated skin conductance responses [ISCR]: area of the galvanic skin responses identified on the signal

PPG:

- Pulsatility index variation (PI): Transit time flow

Breathing belt:

- Breathing rate by cycles per minute

EGG:

- Dominant power
- Total power [0-0.15 Hertz]
- Slow-waves frequency per minute

EEG:

- Spontaneous brain rhythms: spectral power of the 0-30 Hertz band

Physiological adaptation to the aversive situation (emotional reactivity task):

HRV, GSR and PPG differences will be calculated to measure the physiological changes causing by the task compared to the resting and the recovery periods. The differences will be calculated as follows:

- Physiological reactivity during the task compared to the resting period (Δ = reactivity HRV – resting HRV / Δ = reactivity GSR – resting GSR / Δ = reactivity PPG – resting PPG)
- Physiological recovery following the task (Δ = recovery HRV – reactivity HRV / Δ = recovery GSR – reactivity GSR / Δ = recovery PPG – reactivity PPG)

- Physiological recovery following the task compared to the resting period (Δ = recovery HRV – resting HRV / Δ = recovery GSR – resting GSR / Δ = recovery PPG – resting PPG)

Psychological variables:

- Alexithymia score (BVAQ-B)
- Neuroticism score (BFI-N)
- Trait anxiety score (STAI Y-B)
- Style of coping (Brief Cope)
- Positive affectivity score (PANAS)
- State anxiety score (STAI Y-A)
- Depressive symptoms score (CES-D)
- Perceived-stress level (PSS)
- Coping flexibility + metacoping scores (CFS + VAS)
- Acceptance score (ICQ-18)
- Social support score (SSQ6)
- Interceptive sensitivity score (MAIA-2)
- Life satisfaction score (SWLS)
- Negative impact scores (LES)
- Frequency, severity and intensity scores (DHS)
- Abuse scores (CTQ)

Statistical analyses

All statistical analyses will be performed using IBM SPSS Statistics®, R software® and JASP®. The alpha value for statistical significance will set at $p<0.05$.

Analyses of the scores collected will be done in several stages:

- Highlighting outlier participants to exclude from our statistical analysis.
- All the conditions for application of statistical tests will be verified.

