- In the case of a failure to respect the conditions for parametric test application, we would make a data transformation to jointly improve normality and homogeneity residues. If the normality is failed and the homogeneity is respected, we would execute non-parametric tests.
- Analysis will be done on the subjects included. Analysis concerning the reactivity period (during the task) will be performed on the all blocs excepted the bloc 1².
- Main and secondary judgment criterions analysis will be performed by parametric tests or by non-parametric tests depending on the conditions for application:

• *Analyse A:*

- An ANOVA to repeated measurement with an intra factor (measurement time: T1 / T2 / T3) and an inter factor (group: experimental / control) on the physiological and psychological data collected.
- Student's test for independent samples will be performed on the psychological scores collected in the second session (T2) to account for the initial level of psychological states between the 2 groups.

² The bloc 1 will not be included in the final statistical analysis because is considered as a training bloc. This choice in accordance to the potential biases related to the increase of the sympathetic activity at the beginning of the task caused by a simple moving to action following the resting period.

- Contrasts will then be made by group on the scores in order to specify the effect of the condition on the physiological and psychological data.
- *Analyse B:*
 - K means non-hierarchical clustering will be performed with K = 2. To categorise participants depending on their resting neurovegetative profile (low vagal tone / high vagal tone) and on their dynamical neurovegetative profile (low vagal flexibility / high vagal flexibility), two K means non-hierarchical clustering will be performed with K = 2. One with HF or RMSSD and one with Δ HF or Δ RMSSD.
 - Student's test for independent samples (dysfunctional neurovegetative profile / functional neurovegetative profile) will be performed on the psychological vulnerability (trait scores) collected.
- *Analyse C:*
 - An ANOVA to repeated measurement with an intra factor (measurement time: T2 / T3) and an inter factor (neurovegetative profile: dysfunctional profile / functional profile) on the physiological and psychological data collected only into the experimental group performing the BFB technique.
- *Correlational analysis:*

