 - Regressions or the Pearson correlations will be performed in order to measure the inter-signal correlation (ECG-EGG-EEG)
 - Regressions or the Pearson correlations will be performed in order to test our hypothesis about the HF/RMSSD related to the "low vagal tone" profile will be more correlated to Δ HF/RMSSD related to the "low vagal flexibility" profile than to Δ HF/RMSSD related to the "high vagal flexibility" profile. As the same as HF/RMSSD related to the "high vagal tone" profile will be more correlated to Δ HF/RMSSD related to the "high vagal flexibility" profile than to Δ HF/RMSSD related to the "low vagal flexibility" profile

Additional analyses

- We will control the age effect and the gender effect.
- Some additional statistical analyses will be exploratory: stability of the resting and the dynamical neurovegetative endophenotypes before the control period (T1) and at the end of the control period (T2).
- Correlation between the LF 0.1Hz and the clinical outcomes.
- To confirm the physiological effects of the BFB (BFB vs pseudo-BFB) on the flexibility of the electrophysiological coupling concerning the brain-visceral axis.

Sample

Power analysis (G * Power; Faul et al., 2007) was performed to determine a priori the sample size needed for this study. The power analysis, for an ANOVA (repeated measures, within-between factors), was performed for an effect size (η_p^2) of .12 with a power of .95 on the main judgment criterion (HRV – vagal tone HF) and reported a necessary sample of at least 22 participants (Kudo et al., 2014; Paul & Garg, 2012; Wells et al., 2012). We decided to include at least 25 IBS patients SII (20 test & 5 control) and 22 PNES patients (20 test & 5 control) in accordance with the possible inclusion rate and the duration of the study.

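### The PNES target of 22 in the Sample section contradicts its own split (20 + 5 = 25) and the 50 participants implied by the allocation paragraph

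*Combined protocol and SAP*

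**What the plan says.** The SAP's Sample section gives the target as "25 IBS patients SII (20 test & 5 control) and 22 PNES patients (20 test & 5 control", introduced as a minimum. The reason attached to these numbers is that they are "in accordance with the possible inclusion rate and the duration of the study". The sentence before it reports a power analysis "with a power of .95 on the main judgment criterion" (HF heart rate variability), which "reported a necessary sample of at least 22 participants".

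The study protocol, in its paragraph on the intervention period, fixes the allocation by order of entry: "The first 40 participants (20 IBS / 20 PNES) will be included into the experimental group (BFB training", and "the last 10 participants (5 IBS / 5 PNES) will be included into the control group (no training". It does not print a total.

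**The concern.** One of the two diagnostic groups has a stated target that disagrees with the split printed beside it and with the allocation paragraph. The sample size is a figure that the trial relies on for recruitment, allocation and reporting, so it should read the same wherever it appears.

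The order-of-entry rule gives the slip some practical weight. Controls are the last participants to enter, so if someone took 22 as the PNES stopping point, the missing patients would come from the smaller arm.

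**Working it through.** **Head count.** All inputs come from the Sample section and the intervention-period paragraph.

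| Source | IBS | PNES | Total |
|---|---|---|---|
| Sample, stated targets | 25 | 22 | 25 + 22 = 47 |
| Sample, bracketed splits | 20 + 5 = 25 | 20 + 5 = 25 | 50 |
| Protocol, allocation paragraph | 20 + 5 = 25 | 20 + 5 = 25 | 40 + 10 = 50 |

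Only the 22 disagrees. The gap is 3 patients.

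**If PNES recruitment stopped at 22.** Assume that IBS reaches 25 and that the order rule is applied within each diagnosis. The first 20 PNES patients go to BFB, leaving 22 − 20 = 2 PNES controls. The control arm is then 5 + 2 = 7 instead of 10. With equal variance in the two arms, the standard error of the BFB-control difference is proportional to sqrt(1/n1 + 1/n2):

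- 40/10: sqrt(1/40 + 1/10) = .354
- 40/7: sqrt(1/40 + 1/7) = .410; ratio to 40/10 is 1.16
- 37/10 (the 3 missing from BFB instead): sqrt(1/37 + 1/10) = .356; ratio 1.01 (a rise of 0.8%)

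**The plan's own power figure.** Inputs from the documents are partial eta-squared .12, power .95 and N = 22 (Sample). For alpha, Statistical analyses says "The alpha value for statistical significance will set at" .05. Analyse A gives the layout as "an intra factor (measurement time: T1 / T2 / T3) and an inter factor (group: experimental / control", that is, 2 groups and 3 times. Assumptions not in the documents are that the group-by-time interaction is tested, the groups are equal, the correlation between repeated measures is .5, sphericity holds, and the effect-size convention is the one in the formula below.

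- f² = .12/.88 = .1364
- noncentrality λ = f² × N × 3/(1 − .5), with degrees of freedom 2 and 2(N − 2)
- N = 20: λ = 16.4, power .944
- N = 22: λ = 18.0, power .964

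So 22 is the smallest even N that reaches .95, and the plan's figure reproduces. These settings are inferred, not proven. For example, a correlation of .6 with a sphericity epsilon of .75 also gives 22 (power .963).

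**Power at the possible head counts.** Under the same settings, λ is multiplied by 4·n1·n2/N² to allow for unequal arms:

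- 40/10: factor .64, power .997
- 37/10: factor .67, power .996
- 40/7: factor .507, power .980

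All three exceed .95.

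**The case against.** The strongest defence is that the plan does settle the number. The allocation paragraph and the bracket in the Sample section both give 20 + 5 PNES, and the total of 50 follows. Only one printed figure dissents. The same figure, 22, is the power result in the sentence before, so a carry-over slip is plausible, although the documents do not say so. This part stands. A reader might infer that the plan leaves the number of PNES patients open; with two splits agreeing on 25, that goes too far.

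A second defence is that the target is worded as a minimum, so enrolling 25 would satisfy it. As a practical matter that is fair: 22 need not be a stopping point, and a control arm of 7 would itself depart from the allocation paragraph. But it does not repair the sentence, because a minimum of 22 cannot be made up of 20 and 5. The inclusion-rate and duration reason does not explain a lower PNES figure either, since the split beside it is the same as for IBS.

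It also stands that the 16% figure is conditional. It needs recruitment to stop at exactly 22, IBS to reach 25, and the whole shortfall to fall on controls.

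**Conclusion.** The PNES target is wrong as written and should be corrected. It says 22 where its own split and the allocation paragraph give 25, and the stated targets total 47 where the splits total 50. This rests on addition alone. The consequence is modest: at worst, on the assumptions above, 3 controls lost and a standard error about 16% wider, and under 1% wider if the loss falls on the BFB group.

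Two stronger readings are tempting, and the documents support neither.

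- *The trial is underpowered.* On the settings that reproduce the plan's 22, every possible head count keeps power above .95. If .12 is read as the partial eta-squared that ANOVA output would report, 40/10 gives .90 or .72 (with sphericity), depending on whether the value is the one expected in this design or comes from equal-group studies. The documents do not settle which convention applies, so these figures do not establish a shortfall.
- *The power result of 22 is wrong because the allocation is 4:1.* On the same settings, 22 participants split 4:1 would have power of about .84. But the plan does not enrol 22 in total, and the Sample section does not say that the effect tested was the group-by-time interaction. With two groups, a time main effect gives the same 22 on this convention.

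The power sentence does lack detail. The effect tested, correlation, sphericity, effect-size convention and allocation are not stated. That is a reporting gap, not an error.

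**What to change.** In the Sample section, state: 25 IBS (20 BFB, 5 control) and 25 PNES (20 BFB, 5 control), 50 in total. If 22 PNES patients are really intended, give a split that sums to 22 and change the allocation paragraph in the study protocol to match.

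The cost is one corrected number and a stated total. No patients are needed beyond the 50 already in the allocation paragraph, and the design does not change.

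Optional: keep the power sentence and add its settings, namely the effect tested, the correlation between repeated measures, the sphericity assumption, the effect-size convention and the allocation, so that a reader can check it. This is text only.
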